### **6.2 Endpoints**

#### **6.2.1 Primary Endpoint**

Safety Endpoints

- The incidence and severity of adverse events (AE)
- The incidence of serious adverse events (SAE)
- Changes in vital signs
- Changes in physical and neurological exam findings
- Changes in body mass
- Changes in electrocardiogram (ECG) findings
- Changes in clinical laboratory testing (serum chemistry, hematology, urinalysis)
- Changes in the Columbia Suicide Severity Rating Scale (C-SSRS)

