### ***17.4 Data Analysis***

All descriptive statistical analyses will be performed using SAS statistical software (Version 9.3 or higher), unless otherwise noted. AEs will be assessed by the investigator for severity and will be coded for summarization using Medical Dictionary for Regulatory Activities (MedDRA® Version 10.1 or higher). Concomitant medications will be coded using WHO Drug Dictionary (enhanced) Format C, 15 Aug 2005 or more recent updated version.

Adverse events will be summarized by system organ class and preferred term, for each dose group (including placebo) and the incidence compared. Laboratory measures will be summarized by treatment group and time-point both as absolute values and as change from baseline, with descriptive statistics summarizing each group and time point. Similar presentation will be used for vital signs and for ECG interval measurements, and changes from pre-treatment baseline.

Distribution of the data will be characterized, followed by the most appropriate parametric or nonparametric procedures. Comparability of the treatment and placebo groups with respect to

demographic characteristics will be assessed. Appropriate safety tabulations and comparisons across treatment groups will be prepared.

Change from baseline in the composite scores, certain clinical outcome measures, and certain imaging parameters will be analyzed using a mixed model for repeated measures (MMRM), with treatment group as the main effect, visit, baseline score, and treatment by visit as an interaction term. The primary analysis will include post-baseline visits up to Month 6. For scales and parameters with Month 12 data, the model may be run a second time with data through the Month 12 visit. Additional covariates will be considered and will be detailed in the final SAP.

The analysis methodology described above will be used to perform the following comparisons:

- Pooled analysis: for the outcome of interest, the low and high CT1812 dosed groups will be pooled and compared with the placebo group.
- Analysis by arm: for the outcome of interest, each separate CT1812 dose group and placebo group will be compared.

For parameters with only post-baseline visit, an analysis of covariance model (ANCOVA) with treatment group as the main effect and baseline score will be run in place of the MMRM model.

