4.3. Study Design

This is a single-center, Phase 1b, randomized, double-blind, placebo-controlled, parallel-group trial in adults with mild to moderate AD.

After consenting to participate in the study, screening procedures will occur between Days -60 and -1. Eligible participants will be randomized in a 1:1:1 (300 mg active: 100 mg active: placebo) ratio. The first dose of study drug will be administered in the clinic after all baseline procedures have been conducted. For the remainder of study days, participants will ingest study drug each morning at home. Participants and their study partners will return to the clinic for repeat psychometric/neurologic testing, safety studies, and PK and PD sample collection approximately every 2 weeks for the first 6 weeks and then every 3 weeks thereafter up to 24 weeks for the primary study followed by an optional double-blind extension treatment period of an additional 24 weeks (337 days +/-2) as well as a follow up visit at 2 weeks after the final treatment visit

Participants who prematurely discontinue the study for any reason will be asked to attend a final safety and efficacy visit.

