8.2. Safety Data Presentation and Analysis

All clinical safety and tolerability data will be listed for each subject.

Safety data will be summarized using descriptive statistics. Where summaries include changes from baseline, the relevant baseline value will be determined as described in Section 5.5 above.

All treatment-emergent adverse events reported in this study will be listed using MedDRA terms, as coded per the Data Management Plan. The number of subjects reported with AEs and the number of AEs reported following administration of the IP will be summarised by treatment, grouped according to system organ class and preferred term, using descriptive statistics. The order for system organ class will be according to the Internationally Agreed Order, as per the guidance document MedDRA® *Data Retrieval and Presentation: Points to Consider*, specific to the MedDRA version used for this study. Summaries of AEs will also be presented by severity and by relationship to investigational product. In these summaries, subjects will be counted only once per MedDRA term, for the AE of highest severity or least favourable relationship. Summaries will also be presented of SAEs and of AEs leading to study withdrawal.

Clinical laboratory parameters for clinical chemistry, hematology, coagulation, urinalysis and thyroid tests will be listed and summarised by treatment group and study timepoint. Medical assessments of blood and urine parameters will be summarised by treatment group and study timepoint. A summary of changes from baseline will also be presented for serum clinical laboratory parameters. Individual subject profiles will be presented for any laboratory parameters with at least one post-dose value outside the laboratory's reference ranges and deemed clinically significant.

Vital signs will be listed and summarised by treatment and study timepoint. A summary of changes from pre-dose baseline will also be presented.

Body mass will be listed and summarised by treatment and study timepoint. In addition, a summary of changes from pre-dose baseline will be presented.

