9.3. Efficacy Analysis

The change from baseline in the composite scores and clinical outcomes will be analyzed using a mixed effects model including fixed effects for treatment group (i.e. 300 mg active, 100 mg active, placebo), visit and treatment by visit interaction. In addition, the subject's baseline score will be included as a covariate. For each time point up to and

including 6-months, the treatment differences between 300 mg active and placebo, and 100 mg active and placebo will be estimated from the model. In addition, the low and high CT1812 dosed groups will be pooled and compared with the placebo group. This analysis will be considered the primary analysis.

A separate pooled analysis and analysis by arm will also be performed for time points up to and including the 12-month time point.

Additionally, p-values and corresponding two-sided confidence intervals will be provided. The LS Mean Change from Baseline in ADAS-Cog total scores with 95% CI will be presented graphically by treatment group over time.

In the event that a scale or parameter only has a single post-baseline timepoint, an ANCOVA model will be run in place of the MMRM model without the visit and visit by treatment interaction terms. The ANCOVA model will include a fixed effect for treatment group, and the subject's outcome at baseline as a covariate. For parameters for which there are multiple post-baseline timepoints, ANCOVA models such as that just described above may also be run in addition to the MMRM model at various timepoints.

The change from baseline in the ADAS-Cog (sub) scale total score, total time (in seconds) taken to complete both Trail A and Trail B in the NTB, ADCS-ADL total score, MMSE, CDR-SB, and composite scores will be analysed using the MMRM model described above.

To compare 300 mg active vs placebo and 100 mg vs placebo statistically, observed values for ADCS-CGIC will be analyzed using the MMRM model described earlier without the baseline term. Additionally, frequencies and percentages in the ADCS-CGIC will be summarized by visit. Cochran-Mantel-Haenszel mean score statistics, using rank scores will be used to assess the difference in ADCS-CGIC responses at each visit between the CT1812 dose levels and placebo.

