14.3 Safety Data Summaries

14.3.1 Adverse Event Summaries

- Table 14.3.1.1 Overall Summary of Treatment-Emergent Adverse Events by Treatment
- Table 14.3.1.2 Summary of Treatment-Emergent Adverse Events by MedDRA Term and Treatment
- Table 14.3.1.3 Summary of Treatment-Emergent Adverse Events by Intensity (Severity) and Treatment
- Table 14.3.1.4 Summary of Treatment-Emergent Adverse Events by Relationship and Treatment
- Table 14.3.1.5 Summary of Treatment-Emergent Adverse Events of at least Moderate Intensity and Related to Study Treatment, by Treatment

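### The adverse event tables define no reporting period and no exposure adjustment although planned dosing is 24 or 48 weeks, so crude incidence by arm is distorted to the extent that extension uptake differs

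*SAP*

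**What the plan says.** Protocol 5.1 makes safety and tolerability the only primary objective, and AE incidence and severity is the first endpoint listed in 6.2.1. Protocol 17.4 plans a comparison: "Adverse events will be summarized by system organ class and preferred term, for each dose group (including placebo) and the incidence compared".

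SAP 8.2 defines the tables. It says that "All treatment-emergent adverse events reported in this study will be listed using MedDRA terms", and that "The number of subjects reported with AEs and the number of AEs reported following administration of the IP will be summarised by treatment". The population is everyone dosed (SAP 6.1). SAP 5.5 flags an event as treatment-emergent if its onset is at or after the first dose. The flag has no end date and stands under a single-period heading. The shells in SAP Appendix 2, from "Overall Summary of Treatment-Emergent Adverse Events by Treatment" (Table 14.3.1.1) to Table 14.3.1.5, and the serious-event, withdrawal and death tables (14.3.2.1 to 14.3.2.3), carry no period label and no rate.

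Follow-up is not uniform. SAP 4.3 describes 24 weeks of treatment "followed by an optional double-blind extension treatment period of an additional 24 weeks".

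Other outcomes are handled differently. The efficacy model uses data to 6 months, and then "A separate pooled analysis and analysis by arm will also be performed for time points up to and including the 12-month time point" (SAP 9.3). Imaging (SAP 10) and CSF biomarkers (SAP 11.7) follow the same pattern. Laboratory values, vital signs and ECG are summarised by time point (SAP 8.2).

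**The concern.** A participant who takes the extension has about twice as long to report a first event as one who stops at 24 weeks. The tables count both in one denominator. The severity table takes each participant's worst grade per term, so longer observation also gives more chances of a worse grade.

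Entering the extension is a choice made after about 24 weeks on blinded treatment, and it can depend on how well the treatment was tolerated. If participants in a poorly tolerated arm tend to stop at 24 weeks, that arm has less time to accumulate events, and its crude incidence falls relative to an arm whose participants carry on. The distortion could then favour the less tolerated arm, in the tables that report the primary endpoint.

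**Working it through.** **1. The plan's own durations.** Protocol 8.2 gives total participation of up to 36 weeks without the extension and up to 60 weeks with it. Adding the screening period, the last treatment day, the 7-day visit window in Tables 1 and 2, the 14-day follow-up and its 2-day window reproduces both:

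- Primary only: 60 + 169 + 7 + 14 + 2 = 252 days = 36 weeks.
- With extension: 60 + 337 + 7 + 14 + 2 = 420 days = 60 weeks. The permitted gap of up to 4 weeks before the extension is not included.

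Planned dosing is 168 versus 336 days, a ratio of 2.0. First dose to the follow-up visit runs to Day 183 versus Day 351, a ratio of 351/183 = 1.92.

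**2. Person-time per arm.** With 7 per arm (Protocol 17.2) and k of 7 continuing, planned person-weeks are 24 × 7 + 24k. This is 168 for k = 0, 216 for k = 2, 312 for k = 6 and 336 for k = 7. The crude percentage uses 7 as denominator in every case. The count of events has no denominator at all: at an equal, constant event rate, 6 versus 2 continuing gives 312/216 = 1.44 times as many events.

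**3. Effect on crude incidence with no drug effect.** Three inputs are assumed because the documents do not give them: the 24-week risk p, the uptake k, and a constant hazard equal in all arms. Then:

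- Risk by 48 weeks: 1 − (1 − p)².
- Crude incidence in an arm: p + p(1 − p) × k/7.
- Gap between two arms: p(1 − p) × (k₁ − k₂)/7.

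For p = 0.30 the 48-week risk is 1 − 0.49 = 0.51. With 6 of 7 continuing, (1 × 0.30 + 6 × 0.51)/7 = 0.48. With 2 of 7, (5 × 0.30 + 2 × 0.51)/7 = 0.36. The gap is 0.12, or 0.12 × 7 = 0.84 of one participant.

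| Assumed 24-week risk | 48-week risk | 6 of 7 vs 2 of 7 continue | Gap | Gap at 7 of 7 vs 0 of 7 |
|---|---|---|---|---|
| 10% | 19% | 17.7% vs 12.6% | 5 points | 9 points |
| 20% | 36% | 33.7% vs 24.6% | 9 points | 16 points |
| 30% | 51% | 48% vs 36% | 12 points | 21 points |
| 50% | 75% | 71% vs 57% | 14 points | 25 points |

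If k₁ = k₂ the gap is exactly zero.

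**4. Is unequal uptake unusual?** If each participant continues with probability 50% (assumed) and independently, two given arms of 7 have the same number continuing with probability C(14,7)/2¹⁴ = 3432/16384 = 21%. For all three arms it is about 5%. Some imbalance is therefore likely by chance alone, though this says nothing about its size or direction.

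**5. Effect of the remedies, same assumptions.** A cut-off at 24 weeks for everyone gives 30% in both arms whatever the uptake. For a whole-study rate, the weekly hazard is −ln(0.70)/24 = 0.01486. Expected participants with the event over person-weeks at risk is 3.36/226.1 with 6 continuing and 2.52/169.6 with 2 continuing, both 1.49 per 100 person-weeks.

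**The case against.** A reader might infer that the tables set a 24-week arm against a 48-week arm. The documents do not support that. No arm is assigned either duration. The extension is open to all three randomised arms and stays double-blind and placebo-controlled, so each arm is a mixture. Nor does the SAP state that AEs are pooled over the whole study. That follows from the open-ended treatment-emergent flag and the absence of any cut-off, so it is a gap in specification.

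The illustration is also open to challenge. The uptake split is chosen to be unfavourable. If first events cluster early in treatment, the extension adds fewer of them and the gap shrinks. At this sample size the artefact is small beside chance: using 48% and 36%, the standard error of the difference is √[(0.48 × 0.52 + 0.36 × 0.64)/7] = 26 points, so 12 points is under half a standard error. Safety is descriptive, with no AE test or threshold to overturn.

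Finally, much can be recovered. Exposure and completion are summarised by arm (SAP 7.1; Tables 14.1.1 and 14.1.3), AEs leading to withdrawal have their own table, and time since first dose is derived for every AE (SAP 5.5). With about 21 participants a reader could rebuild 24-week counts from the listings.

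All of this bears on size and urgency, and it stands. It does not remove the point. None of these items enters an AE denominator, and the comparison the protocol plans is made from the tables. Chance imprecision cannot be avoided in arms of 7, whereas this component can be removed.

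**Conclusion.** The point holds in a conditional form. As planned, AE incidence by arm refers to no defined period, and the comparison between arms is distorted only as far as extension uptake differs. With equal uptake there is no between-arm bias, although the incidence still has no stated time frame.

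The 12 points (5 to 14 for 24-week risks of 10% to 50%) show the mechanism and do not estimate the bias. They rest on assumed uptake, assumed risk and a constant hazard, and amount to at most one participant in an arm of 7. A reader might also conclude that the drug will look falsely safe. The documents give no uptake by arm, so neither direction nor size can be stated.

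The gap is specific to the AE and SAE tables, because the other safety measures are summarised by time point. It should be fixed because these tables carry the primary endpoint and the remedy is cheap. It does not invalidate the trial.

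**What to change.** In SAP 8.2 and Appendix 2:

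1. Make the main AE and SAE tables (14.3.1.1 to 14.3.1.5 and 14.3.2.x) cover first dose to one cut-off that is the same for all participants regardless of extension entry, for example the Day 169 visit. A window ending at the follow-up visit for some and at the first extension dose for others would still depend on the choice to continue.
2. Tabulate later events separately. Use extension entrants as the denominator for extension-period events, and show post-treatment follow-up events of non-continuers apart.
3. For the whole study, add an exposure-adjusted rate by arm: participants with the event divided by person-time at risk. Treat it as supportive, because it is easy to interpret only if the hazard is roughly constant.

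Two inconsistencies should be reconciled at the same time. Protocol 15.2.1 limits treatment-emergent events to the treatment period, while SAP 5.5 sets no end. The extension visit lists in Protocol 10.2.14 to 10.2.17 mention recording only SAEs, while Table 2 marks AE recording at those visits. If capture differs by period, pooled counts are harder still to interpret.

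The cost is SAP wording and reruns of existing tables by period. Onset and dosing dates are already collected, so no new data are needed. The cut-off is best fixed before unblinding.

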### **4.3 Clinical Experience**

CT1812 has been administered safely with good tolerability in over 60 healthy volunteers in a placebo-controlled Phase 1a trial (COG0101). Six single and three multiple dose cohorts (QD, 14 days) were observed under close inpatient stay (N=6-8 treated, 2 placebo per cohort). Plasma concentrations of drug were shown to be approximately dose proportional across two orders of magnitude [0.13-14.93 mg (free base equivalent)/kg], and accumulation was minimal. Peak concentrations of CT1812 were reached within 1 to 2 hours and the plasma half-life was shown to be approximately 12 hours. Adverse events were mostly mild to moderate in severity and principally included headache, nausea, vomiting, diarrhea, constipation, abdominal pain, dyspepsia, upper respiratory tract infection, lightheadedness, syncope, myalgia, dizziness, rash and pain at the lumbar puncture site in those subjects who had lumbar punctures. There was only one AE of severe intensity, being an SAE of upper respiratory tract infection, occurring in one subject in the 840 mg dose of the multiple ascending dose (MAD) study, believed to be unrelated to study drug based on a similar pattern of URTIs in subjects receiving drugs other than CT1812 in the study unit during the same time period. One subject in the multiple dose cohort study developed a rash while on study drug. This subject showed improvement after discontinuing CT1812.

No evidence of renal toxicity has been observed to date based on routine measures of renal function (serum creatinine, blood urea nitrogen [BUN]) or cystatin C.

Four subjects in the MAD study showed an increase in liver function tests below 3X the upper limit of normal (including one subject on placebo). Subsequent studies will closely monitor liver enzyme parameters to determine if these were sporadic findings or possibly drug-related.

In COG0103 15 healthy volunteers evaluated potential effects of CT1812 on the disposition of sensitive substrates of selected CYP isoenzymes CYP2C19 (omeprazole), CYP2C9 (tolbutamide), CYP2D6 (dextromethorphan), and CYP3A4/5 (midazolam). Subjects were administered the probe drugs on Day -2 and pharmacokinetic (PK) evaluations performed. On Days 1 through 6, each subject took CT1812 560 mg. The CT1812 dose on Day 6 was taken

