#### **FOR INDIVIDUAL PARTICIPANTS:**

Participants who develop a severe adverse event or laboratory abnormality will not receive any additional doses and will be monitored until resolution of the AE or the return of laboratory abnormality to the acceptable screening value(s). Study drug may be re-initiated after consultation with medical monitor and sponsor. Any participant with:

- elevated ALT or AST greater than 5 X ULN should have dosing with study drug stopped and have laboratory tests repeated every 3-4 days until levels return to less than or equal to 1.5 X ULN. If the medical monitor and investigator are in agreement, study drug may be continued while a confirmatory ALT/AST is obtained within 3 days. If the confirmatory ALT/AST tests are below 5 X ULN, study drug may be continued. The frequency of the laboratory tests may be modified after discussion with the medical monitor if the liver enzymes are in a decreasing trend.
- Elevated ALT or AST greater than 3 X ULN in combination with total bilirubin > 2 X ULN or INR > 1.5 X ULN OR an ALT or AST > 3 X ULN with the appearance of fatigue, nausea, vomiting, right upper quadrant pain or tenderness, fever, rash, and/or eosinophilia (>5%) should have dosing with study drug stopped and have laboratory testing repeated every 3-4 days. If the medical monitor and investigator are in agreement, study drug may be continued while a confirmatory laboratory testing is obtained within 3 days. If these criteria are no longer met, study drug can be continued at the discretion of the medical monitor and investigator. The frequency of the laboratory tests may be modified after discussion with the medical monitor if the laboratory tests are trending towards normal.
- An increase in serum creatinine by 0.3 mg/dL (24.4 micromol/L) or 150% of baseline that is without clinical explanation of another etiology will result in repeated serum chemistry testing within 3-7 days. If the serum creatinine elevation is confirmed on repeated testing the study drug will be discontinued. If the serum creatinine elevation resolves upon

subsequent testing after study drug is discontinued the study drug may be restarted with serum creatinine monitoring at the discretion of the medical monitor and investigator.

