5.5. Data Derived by Calculation

The following data fields for inclusion in the data listings will be derived by calculation:

AEs Single Period:

- Treatment-emergent Indicator for adverse event, assigned as Treatment-Emergent if

$(\text{Onset Date} + \text{Onset Time}) \geq (\text{Date of First Dose} + \text{Time of First Dose})$

Non Treatment-Emergent if

$(\text{Onset Date} + \text{Onset Time}) < (\text{Date of First Dose} + \text{Time of First Dose})$

- Adverse event time since first dose (in days, to two decimal places), calculated as $(\text{Onset Date} + \text{Onset Time}) - (\text{Date of First Dose} + \text{Time of First Dose})$
- Adverse event time since dose in current treatment period (in days, to two decimal places), calculated as $(\text{Onset Date} + \text{Onset Time} - \text{Date of Dose in Current Treatment Period} - \text{Time of Dose in Current Treatment Period})$

AE Duration:

- Adverse event duration (in days, to two decimal places), calculated as $(\text{Resolution Date} + \text{Resolution Time} - \text{Onset Date} - \text{Onset Time})$

Safety Assessments Change from Baseline:

- Baseline for Vital Signs, ECG parameters, serum clinical laboratory parameters will be the most recent scheduled assessment prior to first dose

Clinical Laboratory Assessments:

- If a clinical laboratory result is above the upper limit of normal, then Out of Range flag will be set to “H”
- If a clinical laboratory result is below the lower limit of normal, then Out of Range flag will be set to “L”
- Clinical Laboratory parameters that are outside the reference range and assessed as clinically significant will be identified as “Abnormal CS”
- Clinical Laboratory parameters that are outside the reference range and not assessed as clinically significant will be identified as “Abnormal NCS”

Pharmacokinetics:

- Actual collection time post-dose (in hours, to two decimal places) for PK blood samples for each dose day calculated as $(\text{Collection Date} + \text{Collection Time} - \text{Date of Dose} - \text{Time of Dose})$

Pharmacodynamics:

- Actual collection time post-dose (in hours, to two decimal places) for PD CSF samples for each dose day calculated as $(\text{Collection Date} + \text{Collection Time} - \text{Date of Dose} - \text{Time of Dose})$

Efficacy Assessments Change from Baseline:

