ECG parameters will be listed and summarised by treatment and study time point. A summary of changes from pre-dose baseline will also be presented. For QTcB the number of subjects with values greater than 450 (and 480, 500) msec or an increase from baseline of at least 30 (and 60) msec will also be presented, in accordance with ICH E14 (Note for guidance on the clinical evaluation of QT/QTc interval prolongation and proarrhythmic potential for non-antiarrhythmic drugs, CHMP/ICH/2/04).

Changes in physical examination findings over time will be listed by body system for each subject. It is noted that any untoward findings identified on physical examinations after the administration of the first dose of study medication will be captured as an adverse event if those findings meet the definition of an adverse event as defined in the protocol.

Changes in neurological examination findings over time will be listed by neurological system for each subject.

Changes in the Columbia Suicide Severity Rating Scale (C-SSRS) will be listed for each subject.

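### SAP 8.2's profile rule can miss a creatinine rise that meets protocol 7.3.1 within the reference range, and no planned table counts participants at the 7.3.1 laboratory criteria by arm

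*SAP*

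**What the plan says.** **Profiles and flags.** SAP 8.2 sets two conditions for an individual laboratory profile: "Individual subject profiles will be presented for any laboratory parameters with at least one post-dose value outside" "the laboratory's reference ranges and deemed clinically significant". SAP 5.5 builds the first condition into the label itself: "Clinical Laboratory parameters that are outside the reference range and assessed as clinically significant will be identified as" 'Abnormal CS'. The high flag is set only when a result exceeds the upper limit of normal.

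**Other laboratory outputs.** SAP 8.2 also plans full listings, descriptive summaries and medical assessments by arm and timepoint, and a change-from-baseline summary for serum parameters. Appendix 2, section 14.3.4, names eight tables.

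**Protocol criteria.** Section 7.3.1 acts on four kinds of laboratory finding in an individual:
- ALT or AST above 5 × ULN.
- ALT or AST above 3 × ULN together with bilirubin above 2 × ULN, INR above 1.5 × ULN, or listed symptoms or eosinophilia.
- "An increase in serum creatinine by 0.3 mg/dL (24.4 micromol/L) or 150% of baseline that is without clinical explanation of another etiology", which prompts a retest; drug is discontinued if the rise is confirmed.
- Calcium of 10.5 mg/dL or more with no other explanation, handled in the same way.

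Drug may be restarted in several of these situations.

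**Comparison.** The SAP does count participants at ECG cut-offs: "For QTcB the number of subjects with values greater than 450 (and 480, 500) msec", plus increases of at least 30 and 60 msec (Table 14.3.6.7). For adverse events it says: "Summaries will also be presented of SAEs and of AEs leading to study withdrawal".

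**The concern.** Safety and tolerability is the only primary objective, and change in laboratory tests is one of its endpoints. The protocol names hypercalcemia and renal tubular damage as dose-limiting in animals (4.2.1, 4.2.3). It also reports an ALT rise to 4.7 × ULN at 560 mg in the earlier Alzheimer's trial, and says of liver enzyme rises: "Subsequent studies will closely monitor liver enzyme parameters to determine if these were sporadic findings or possibly drug-related".

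The laboratory findings that lead to drug being stopped are therefore those a reader will want to see by dose. The planned outputs are organised around a different test (out of range, and judged clinically significant), and no table is built on the protocol's own criteria. With seven participants planned per arm, one participant is 1/7 = 14% of an arm. A count is then easier to interpret than a mean.

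**Working it through.** The plan gives no figure of its own on this point. The check compares the rules, with simple arithmetic for creatinine.

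**1. Can the creatinine criterion be met in range?** The documents do not give the laboratory's creatinine ULN, so 1.0 to 1.4 mg/dL is assumed.
- Absolute limb: baseline + 0.3 ≤ ULN, so baseline ≤ ULN − 0.3.
- Relative limb, if read as reaching 1.5 times baseline: baseline ≤ ULN / 1.5.

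| Assumed ULN (mg/dL) | Highest baseline still in range after +0.3 | Highest baseline still in range at 1.5 × baseline |
|---|---|---|
| 1.0 | 0.7 | 0.67 |
| 1.1 | 0.8 | 0.73 |
| 1.2 | 0.9 | 0.80 |
| 1.3 | 1.0 | 0.87 |
| 1.4 | 1.1 | 0.93 |

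Example: a rise from 0.7 to 1.0 mg/dL meets the 0.3 limb and exceeds none of these limits. Under SAP 5.5 and 8.2 it gets no high flag, cannot be 'Abnormal CS', and triggers no profile, whatever the investigator thinks of it.

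**2. Would the change-from-baseline summary show it?** One participant rising by 0.3 among seven moves the arm mean by 0.3/7 = 0.043 mg/dL.

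**3. The other criteria.**
- ALT or AST above 5 × ULN is always out of range, so only the clinical-significance judgement stands between it and a profile.
- Calcium of 10.5 mg/dL is a fixed cut-off. It could escape in the same way only if the laboratory's ULN lies above 10.5, and the documents do not give that ULN.
- The in-range gap is therefore shown for creatinine only.

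**4. Is any threshold counted by arm?** The tables in 14.3.4 are three result summaries (hematology, chemistry, coagulation), four assessment summaries (the same three plus urinalysis) and one set of profiles: 3 + 4 + 1 = 8. By title and by the text of 8.2, none counts participants at a liver, creatinine or calcium threshold.

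**5. Can the creatinine criterion be programmed as written?** With an assumed molar mass of 113.12 g/mol, 0.3 mg/dL is 0.3 × 10 / 113.12 × 1000 = 26.5 micromol/L. The printed 24.4 micromol/L is 24.4 × 113.12 / 10,000 = 0.276 mg/dL. A rise between 0.276 and 0.3 mg/dL meets one figure but not the other. The relative limb can also be read as a rise to 150% or a rise by 150%.

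**The case against.** The strongest reply is that these events have other ways to surface.
- Protocol 15.2.1 treats a laboratory abnormality serious enough to need active management, including stopping drug or closer follow-up, as an adverse event if clinically significant. It does not require an out-of-range value. A confirmed creatinine rise that stops drug would usually qualify and be counted by arm in Tables 14.3.1.2 to 14.3.1.4.
- Protocol 9.4 includes 7.3.1 events among reasons for withdrawal, which would reach Table 14.3.2.2.
- Every value is listed, for about 21 participants.
- The SAP delivers what protocol 17.4 promises for laboratory data.
- The QTcB categories are there because of ICH E14, so their presence does not show a lapse elsewhere.
- The statement in 4.3 on liver enzymes is about monitoring and does not promise a table.

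All of this stands, and it rules out several stronger readings that a reader might infer:
- That drug-stopping laboratory events go unreported. They may well be reported; they are not counted against the protocol's criteria.
- That the SAP contradicts the protocol. It does not.
- That ALT or AST above 3 × ULN alone is a stopping criterion. Section 7.3.1 has no such rule. The earlier 4.7 × ULN case would meet 7.3.1 only with an accompanying bilirubin, INR, symptom or eosinophilia finding.
- That the case report form's action-taken field identifies drug stopped and restarted. Section 15.2.2.4 offers only none, reduced, or discontinued in the permanent sense.

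What the reply does not remove: the adverse event route depends on a clinical judgement and groups by preferred term. The withdrawal table need not capture participants whose drug is stopped and restarted, which 7.3.1 allows. SAP section 1 labels analyses added on review of unblinded results as post hoc.

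**Conclusion.** The point holds as a cheap reporting improvement. The profile rule excludes any in-range creatinine rise that meets 7.3.1, and no planned table counts participants by arm at the 7.3.1 liver, creatinine or calcium criteria. The first follows from the wording of SAP 5.5 and 8.2. Its reach depends on the assumed ULN: baselines up to 0.7 mg/dL at a ULN of 1.0, and up to 1.1 mg/dL at a ULN of 1.4. The second follows from SAP 8.2 and the table list. No data are lost and no efficacy or power statement is affected. What is at stake is whether a dose pattern in the laboratory findings that stop drug is shown by a pre-specified count or has to be assembled afterwards from listings.

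**What to change.** Amend the SAP before unblinding:
1. Extend the profile trigger in 8.2 to include any participant who meets the laboratory component of a 7.3.1 criterion, in range or not.
2. Add one table by arm and for pooled CT1812, counting participants who ever meet the laboratory component of each 7.3.1 criterion as written:
   - ALT/AST above 5 × ULN;
   - ALT/AST above 3 × ULN with bilirubin above 2 × ULN or INR above 1.5 × ULN, with the symptom and eosinophilia limb taken from adverse event and hematology data;
   - the creatinine rise;
   - calcium of 10.5 mg/dL or more.

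   Include unscheduled retests, and show any occurrence and confirmed-on-repeat separately. ALT/AST above 3 × ULN alone may be added as a descriptive category, which would show a case like the earlier 4.7 × ULN one, but it must not be labelled a stopping criterion. Whether there was another explanation cannot be read from laboratory values, so the title should say 'laboratory component'.
3. If stopping of drug is summarised, take it from the dosing records (Listing 16.2.5.1), because the action-taken field has no code for interruption.
4. Before programming, the sponsor must reconcile the protocol's creatinine wording (to or by 150% of baseline) and its two units (0.3 mg/dL and 24.4 micromol/L).

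The cost is one extra table and a few more profiles, from data already collected. Apart from the creatinine reconciliation, the protocol is untouched, and the proposal changes no dosing or stopping rule.
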